Optional liver biopsy ^h					X				

* Visit windows are \pm 2 weeks for visits in Years 2-5.

^a These assessments need to be performed only at every other Q12W and every End of Year visit (ie, Weeks 76, 104, 128, 156, 180, 208, 232, and 260).

^b Complete physical examination should be performed at the End of Year visits; brief physical exam may be performed at other study visits. Weight should be recorded at the second Q12W visit each year and at every End of Year visit during Years 2-5.

^c Refer to [Table 9.7.8.2.1](#) for laboratory assessments to be included, and to [Table 9.7.8.3.1](#) for liver tests. LTs may be monitored more or less frequently (and in particular when ALT values are $>$ ULN or $\geq 1.5\times$ baseline value) based on discussion between the Medical Monitor and the Investigator and review of subject data, but LTs will be monitored at least twice weekly during periods when a subject's ALT is $\geq 3\times$ ULN. Subjects with ALT $>$ ULN or $\geq 1.5\times$ baseline value during the study and either an alternative etiology considered or for further evaluation of the lab abnormality may undergo additional evaluations (eg, imaging studies including MRI or ultrasound, additional blood tests, and/or liver biopsy) at the discretion of the Investigator. Additional testing of FVIII and LTs during any study week may be performed if: (1) the ALT has increased to $\geq 1.5\times$ baseline value; (2) Increases in ALT values from prior assessment are accompanied by declines in FVIII activity level; or after a discussion between the Medical Monitor and the Investigator based on a review of subject data. If FVIII levels and/or ALT values are stable over the course of several weeks, assessment of FVIII activity and ALT levels may be adjusted based on discussion between the Medical Monitor and the Investigator. During Years 2-5 of the Post-Infusion Follow-Up period, urine tests and blood, chemistry, and coagulation tests should be performed at the second Q12W visit each year and at every End of Year visit. In case of a safety concern, additional unscheduled laboratory tests may be performed locally (at the Investigator's discretion) in order to facilitate timely and appropriate clinical management decisions; where possible, a matched sample for testing at the central laboratory should be collected (using the Unscheduled Visit lab kit) at the same time as the local unscheduled sample

^d Includes FVIII activity level (chromogenic substrate FVIII assay and one-stage clotting FVIII assay), chromogenic Nijmegen-Bethesda Assay for hFVIII inhibitor level, coagulation exploratory assay, and hFVIII protein assay. If a subject has used FVIII within 72 hours of a measurement day, all efforts should be made to obtain FVIII activity measurements when a 72-hour interval without FVIII use is achieved; the 72-hour wash-out period is only intended for subjects who have achieved FVIII ≥ 5 IU/dL at 16 weeks after BMN 270 infusion and who have not resumed FVIII replacement therapy. If FVIII levels are elevated or stable over the course of several weeks, assessment of FVIII activity may be adjusted based on discussion between the Medical Monitor and the Investigator. A D-dimer may be considered under circumstances in which FVIII activity levels are above the normal physiological range and/or if there is a concern for a venous thromboembolism. If a subject tests positive in the Bethesda assay (with Nijmegen modification) during Years 3-5, a fresh sample should be collected within 4 weeks of the initial visit that had a positive result.

^e Sample testing during Years 2-5 is not required if at least 3 consecutive samples were below the limit of detection during Year 1; additional collection and testing may be performed based on batch testing schedules, result turnaround times, or discussions between Medical Monitor and Investigator. Subjects who have not had 3 consecutive semen samples below the limit of

detection by Week 52 should continue to have PCR testing of semen every 4 weeks (during Year 2) or every 6 weeks (during Years 3-5) until 3 consecutive samples below the limit of detection are documented (or upon consultation between the Investigator and Medical Monitor).

^f Blood samples will be collected to evaluate biochemical, molecular, cellular, immunological, and genetic/genomic aspects relevant to hemophilia A, coagulation, and/or AAV gene transfer, and to develop assays used for these evaluations. Subjects may choose to opt out of the exploratory genetic/genomic research being done to study or try to discover genes that are not yet known to be associated with hemophilia A. While exploratory samples will be collected at the time points indicated above, testing of these samples, as well as testing of the TGA assay sample, will be performed only as deemed necessary by the Sponsor.

^g Subjects who meet the definition of treatment failure to BMN 270 therapy after Week 52 may omit the Q4W and Q6W visits during Years 2-5, and must attend only the Q12W and End of Year visits. Subjects who are not attending the Q4W/Q6W visits during Years 2-5 may receive a scheduled monthly follow-up telephone call from the site to ask about adverse events, concomitant medications, and bleeding events/FVIII replacement usage. Such subjects following the abbreviated schedule who have not yet cleared vector shedding in semen must still provide samples Q4W (during Year 2) or Q6W (during Years 3-5) until vector shedding has been cleared, either by reporting to the site to provide samples or by providing those samples to a MN professional. Unscheduled visits may also be conducted by MN as appropriate.

^h An optional liver biopsy may be performed at any time between Years 2-5 of the study. The optional biopsy would be triggered by a FVIII activity decline by > 50% from steady-state, over 2 consecutive measurements, or by a sustained ALT rise > ULN. If neither trigger is observed, the optional biopsy should be performed at the end of Year 5.

Table 9.1.5: Schedule of Events-Optional Liver Biopsy

	Within 28 Days Before Biopsy Day	Within 7 Days Before Biopsy Day	Biopsy Day (BD)
Informed Consent for Liver Biopsy Procedure	X		
Liver Ultrasound ^a	X		
Physical examination	X		X
Hematology, Coagulation, Chemistry Assessments ^b	X		X
Liver Tests ^b	X		X
FibroScan	X		
FV III Activity Level Assessment (central and local)		X	X*
Exploratory CK18 and Grp78 assessment		X	X*
Pre-Biopsy Consultation ^c		X	
Liver Biopsy ^d			X
PBMC Collection (whole blood draw)			X ^e

* If the Day -7 and biopsy day visits occur on the same day, these tests do not need to be duplicated.

^a Liver ultrasound must be performed within 28 days prior to the scheduled biopsy. Subjects should fast for at least 8 hours prior to liver ultrasound.

^b Refer to [Table 9.7.8.2.1](#) for laboratory assessments to be included, and to [Table 9.7.8.3.1](#) for liver tests.

^c Subjects will undergo a pre-biopsy consultation with the Investigator (treating hematologist) and hepatologist and/or radiologist.

^d Subjects should fast for at least 8 hours prior to optional liver biopsy. Biopsy will be a percutaneous or transjugular biopsy under ultrasound guidance, performed according to the standard procedure of the institution. If only a small amount of tissue (< 2 cm) is obtained at the time of the biopsy, the subject may be asked to consent for a second pass. In this case, the original < 2 cm sample should still be retained and handled according to the instructions for handling biopsy specimens in the Laboratory Manual. Following completion of the biopsy, the subject should remain in the hospital under observation for at least 4-6 hours. Overnight post-procedure observation may be done at the investigator's discretion.

^e Blood draw for PBMC collection should be performed on the biopsy day or ± 1 week from the biopsy day.

Table 9.1.6: Suggested Schedule of Events-Prophylactic Corticosteroids

Assessment	D1	Corticosteroid Treatment Period ^b												Post-Corticosteroid Period ^c												
		1	2	3	4	5	6	7	8	9	10	11	12	13	14	15	16	17	18	19	20	21	22	23	32	
Week																										
Prophylactic corticosteroid dose (mg/day)	40 mg	40 mg	40 mg	40 mg	40 mg	40 mg	40 mg	40 mg	40 mg	35 mg	30 mg	30 mg	25 mg	25 mg	20 mg	20 mg	15 mg	10 mg	5 mg							
FVIII activity testing	X	X	X	X	X	X	X	X	X	X	X	X	X	X	X	X	X	X	X	X	X	X	X	X		
Liver tests	X	X	X	X	X	X	X	X	X	X	X	X	X	X	X	X	X	X	X	X	X	X	X	X		
Hepatitis B testing ^d																									X	
HCV Viral Load ^d																									X	

^a This table provides an example of a prophylactic corticosteroid course. Clinical judgment, weighing the potential risks and benefits of corticosteroid treatment, should always be exercised when considering adjustment of corticosteroid doses, and discussions between the Investigator and Medical Monitor are advised for any questions or concerns. Dosages are for prednisone or an equivalent dose of another corticosteroid. FVIII and liver tests are also reflected in the Schedule of Events for the study.

^b Following initiation or completion of corticosteroid regimen, if a recurrence of ALT values $> \text{ULN}$ or $\geq 1.5 \times$ baseline value is reported, corticosteroid management decisions will be based on discussions between the Investigator and Medical Monitor. Modification of the corticosteroid regimen may take into consideration possible confounders for the ALT elevation, relationship between increases in ALT and FVIII activity, ALT levels/FVIII activity post-corticosteroid initiation, and adverse events related to corticosteroid dosing. Guidance for tapering oral corticosteroid dosing can be found in Section 9.4.8.2, although a discussion between the PI and Medical Monitor should take place prior to tapering the corticosteroid dose.

^c After discontinuation of oral corticosteroids, weekly labs for ALT levels and FVIII activity will be measured once a week for 4 weeks to ensure stability in values.

^d Should only be performed in subjects with a history of hepatitis B or hepatitis C prior to study entry. Tests are also reflected in the Schedule of Events for the study.

9.2 Discussion of Study Design

Study 270-303 is a Phase 3b, single arm, open-label study designed to assess whether BMN 270, at a dose of 6E13 vg/kg with prophylactic corticosteroids, can safely and effectively improve the FVIII activity profiles and alter the clinical phenotype of hemophilia A patients with residual FVIII activity ≤ 1 IU/dL. Subjects must have high-quality, well-documented historical data available concerning previous bleeding episodes and exogenous FVIII usage over the previous 12 months in order to be eligible to enroll in the study.

Given that BMN 270 is likely a one-time treatment, due to antibody formation against the AAV5 capsid post-infusion, and the well-characterized clinical experience of patients with severe hemophilia A on currently available chronic therapies, having a separate control group in this study was deemed to be inappropriate and unnecessary, as has been the case with all AAV gene therapy trials to date.

Approximately 20 adult subjects with severe HA will receive a 6E13 vg/kg dose of BMN 270 as a single intravenous infusion in conjunction with receipt of a prophylactic corticosteroid regimen. Post-infusion, subjects will be eligible to receive on-demand corticosteroids, as indicated.

9.3 Selection of Study Population

Approximately 20 adult hemophilia A patients with residual FVIII levels ≤ 1 IU/dL may enroll into the study.

Additional criteria for participation in the study are provided in Section 9.3.1 and Section 9.3.2.

9.3.1 Inclusion Criteria

Individuals eligible to participate in this study must meet all of the following inclusion criteria:

1. Males ≥ 18 years of age with hemophilia A and residual FVIII levels ≤ 1 IU/dL as evidenced by medical history, at the time of signing the informed consent.
2. Must have been on prophylactic hemophilia therapy for at least 12 months prior to study entry. High-quality, well-documented historical data concerning bleeding episodes and hemophilia therapy usage over the previous 12 months must be available.
3. Treated/exposed to FVIII concentrates or cryoprecipitate for a minimum of 150 exposure days (EDs).

4. Willing and able to provide written, signed informed consent after the nature of the study has been explained and prior to any study-related procedures.
5. No previous documented history of a detectable FVIII inhibitor, and results from a Bethesda assay or Bethesda assay with Nijmegen modification of less than 0.6 Bethesda Units (BU) (or less than 1.0 BU for laboratories with a historical lower sensitivity cutoff for inhibitor detection of 1.0 BU) on 2 consecutive occasions at least one week apart within the past 12 months (at least one of which should be tested at the central laboratory).
6. Sexually active participants must agree to use an acceptable method of effective contraception, either double-barrier contraception (ie, condom + diaphragm; or condom or diaphragm + spermicidal gel or foam) or their female partner either using hormonal contraceptives or having an intrauterine device. Participants must agree to contraception use for at least 12 weeks post-infusion; after 12 weeks, subjects may stop contraception use only if they have had 3 consecutive semen samples with viral vector DNA below the limit of detection.
7. Willing to abstain from alcohol consumption for at least the first 52 weeks following BMN 270 infusion.

9.3.2 Exclusion Criteria

Individuals who meet any of the following exclusion criteria will not be eligible to participate in the study:

1. Detectable pre-existing antibodies to the AAV5 capsid. Up to 25% of subjects may have detectable pre-existing AAV5 capsid antibodies, so long as the titer level is below the minimum required dilution (< 20).
2. Any evidence of active infection, including COVID-19, or any immunosuppressive disorder, including HIV infection.
3. Significant liver dysfunction with any of the following abnormal laboratory results:
 - ALT (alanine aminotransferase) > 1.25x ULN;
 - AST (aspartate aminotransferase) > 1.25x ULN;
 - GGT (gamma-glutamyltransferase) > 1.25x ULN;
 - Total bilirubin > 1.25x ULN;
 - Alkaline phosphatase > 1.25x ULN; or
 - INR (international normalized ratio) ≥ 1.4 .

Subjects whose liver laboratory assessments fall outside of these ranges may undergo repeat testing of the entire liver test panel within the same Screening window and, if eligibility criteria are met on retest, may be enrolled after confirmation by the Medical Monitor.

4. FibroScan or prior liver biopsy showing significant fibrosis of 3 or 4 as rated on a scale of 0-4 on the Batts-Ludwig ([Batts, 1995](#)) or METAVIR ([Bedossa, 1996](#)) scoring systems, or an equivalent grade of fibrosis if an alternative scale is used.
5. Evidence of any bleeding disorder not related to hemophilia A.
6. Platelet count of < 100 x 10⁹/L.
7. Creatinine \geq 1.5 mg/dL.
8. Liver cirrhosis of any etiology as assessed by FibroScan or liver ultrasound.
9. Chronic or active hepatitis B as evidenced by positive serology testing (hepatitis B surface antigen [HBsAg], hepatitis B surface antibody [HBsAb], and hepatitis B core antibody [HBcAb]) and confirmatory HBV DNA testing. Refer to the Centers for Disease Control (CDC) table for the interpretation of serological test results in the Laboratory Manual.
10. Active Hepatitis C as evidenced by detectable HCV RNA or currently on antiviral therapy.
11. Active malignancy, except non-melanoma skin cancer.
12. History of hepatic malignancy.
13. History of arterial or venous thromboembolic events (eg, deep vein thrombosis, non-hemorrhagic stroke, pulmonary embolism, myocardial infarction, arterial embolus), with the exception of catheter-associated thrombosis for which anti-thrombotic treatment is not currently ongoing.
14. Known inherited or acquired thrombophilia, including conditions associated with increased thromboembolic risk, such as atrial fibrillation.
15. Treatment with any investigational product within 30 days or 5 half-lives of the investigational product prior to the screening period. For subjects who have received a prior investigational product, all ongoing adverse events (AEs) experienced while receiving that investigational product must have resolved prior to screening for this study.
16. Any condition that, in the opinion of the Investigator or Sponsor would prevent the patient from fully complying with the requirements of the study (including possible corticosteroid treatment and/or use of alternative immunosuppressive agents outlined in the protocol) and/or would impact or interfere with evaluation and interpretation of subject safety or efficacy result.
17. Prior treatment with any vector or gene transfer agent.
18. Major surgery planned in the 52-week period following the infusion with BMN 270.
19. Use of systemic immunosuppressive agents, not including corticosteroids, or live vaccines within 30 days before the BMN 270 infusion.

20. Concurrent enrollment in another clinical study, unless it is an observational (non-interventional) clinical study that does not interfere with the requirements of the current protocol or have the potential to impact the evaluation of efficacy and safety of BMN 270 and with prior consultation with the Medical Monitor.
21. Known allergy or hypersensitivity to BMN 270 investigational product formulation.
22. Unwilling to receive blood or blood products for treatment of an adverse event and/or a bleeding episode.

9.3.2.1 Optional Liver Biopsy Inclusion and Exclusion Criteria

Individuals eligible for the optional liver biopsy must meet the following inclusion criterion:

1. Able to sign informed consent and comply with requirements for the optional liver biopsy
2. Documentation of FVIII activity ≥ 50 IU/dL (or higher, depending on local guidelines and/or Investigator discretion) within 24 hours prior to the liver biopsy being performed (FVIII activity levels should be assessed at the local laboratory). Subjects may be treated with additional exogenous FVIII replacement products in order to increase their FVIII levels activity to an appropriate level, under the supervision/instruction of the Investigator.

Individuals who meet any of the following exclusion criteria will not be eligible for the optional liver biopsy:

1. Any condition that, in the opinion of the Investigator or a hepatologist/radiologist would make liver biopsy contraindicated. This includes (but is not limited to) abnormalities detected on liver ultrasound performed within 28 days of procedure, or prior liver ultrasound result within 90 days that would preclude safe performance of the biopsy.

9.3.3 Removal of Subjects from Treatment or Assessment

Subjects may withdraw their consent to participate in the study at any time without prejudice. The Investigator must withdraw from the study any subject who requests to be withdrawn. Such subjects will always be asked about the reason(s) for withdrawal. The Investigator will discuss with the subject appropriate procedures for withdrawal from the study. The Investigator should ask the subject's consent to perform the procedures listed under the early termination visit. Should a subject withdraw from the study, all efforts will be made to complete and report the observations as thoroughly as possible up to the date of the withdrawal.

A subject's participation in the study may be discontinued at any time at the discretion of BioMarin or of the Investigator and in accordance with his/her clinical judgment. When

possible, the tests and evaluations listed for the termination visit should be carried out and every effort will be made to gather follow-up safety data if possible.

BioMarin must be notified of all subject withdrawals as soon as possible. BioMarin also reserves the right to discontinue the study at any time for either clinical or administrative reasons and to discontinue participation by an individual Investigator or site for poor enrollment or noncompliance.

Reasons for which the Investigator or BioMarin may withdraw a subject from the study include, but are not limited to, the following:

- Subject requires medication or medical procedure prohibited by the protocol
- Subject does not adhere to study requirements specified in the protocol
- Subject was erroneously enrolled into the study or does not meet entry criteria and not yet been dosed with BMN 270; subjects who do not meet entry criteria but who erroneously receive BMN 270 should remain in the study for safety monitoring
- Subject is lost to follow-up

If a subject fails to return for scheduled visits, a documented effort must be made to determine the reason. If the subject cannot be reached by telephone, a certified letter should be sent to the subject requesting contact with the Investigator. This information should be recorded in the study records.

Subjects may be considered lost to follow-up if the subject has missed 3 consecutive visits in the study and has failed to communicate a reason for this to the site. In addition, the site has documented at least 4 attempted contacts by key research personnel to reach the subject without success in the following manner:

- 2 attempts by telephone or email (if possible); then
- If telephone/email contacts are unsuccessful, 2 attempts must be made by certified letter or by appropriate local process.

Where communication has been made by phone, this should be documented in the subject source notes.

The Investigator or designee must explain to each subject, before enrollment into the study, that for evaluation of study results, the subject's protected health information obtained during the study may be shared with the study Sponsor, regulatory agencies, and IRB/IEC. It is the Investigator's (or designee's) responsibility to obtain written permission to use protected health information per country-specific regulations, such as the Health Insurance Portability and Accountability Act (HIPAA) in the US, from each subject. If permission to use protected

health information is withdrawn, it is the Investigator's responsibility to obtain a written request, to ensure that no further data will be collected from the subject and the subject will be removed from the study.

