9.3.4 Subject Identification and Replacement of Subjects

Each subject will be assigned a unique subject identifier. This unique identifier will be on all electronic case report form (eCRF) pages. In legal jurisdictions where use of initials is not permitted, a substitute identifier will be used.

Subjects who withdraw from the study after receiving BMN 270 will not be replaced.

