9.4.8 Prior and Concomitant Medications

All prescription and over-the-counter medications (including dietary and herbal supplements) taken by a subject for 30 days before Screening will be recorded on the designated eCRF.

The Investigator may prescribe additional medications, deemed necessary to provide adequate prophylactic or supportive care, during the study, as long as the prescribed medication is not prohibited by the protocol. In the event of an emergency, any needed medications may be prescribed without prior approval, but the Medical Monitor must be notified of the use of any contraindicated medications immediately thereafter. Any concomitant medications added or discontinued during the study should be recorded on the eCRF. Medications should, whenever possible, not be recorded in the electronic database with a frequency of as needed (PRN).

The following medications are prohibited starting 30 days before Screening and through the end of the study, and the Sponsor must be notified if a subject receives any of these during the study:

- Any investigational therapy
- Fitusiran
- Concizumab
- Efavirenz

The following medications and agents should be avoided, starting 30 days prior to and for at least 52 weeks after BMN 270 infusion and minimized throughout the remaining duration of the study.

- Alcohol
- Herbal and natural remedies and dietary supplements
- Medications which may be hepatotoxic, including isotretinoin and dextroamphetamine/amphetamine
- Medications which may reduce or increase the plasma concentration of corticosteroids

Subjects should be counseled to avoid starting potentially hepatotoxic therapies and to inform the Investigator of any new medications prescribed by other physicians. Investigators should carefully consider both the mechanism of action and potential hepatotoxicity of any new medication prior to initiation. If a potentially concerning new medication is started, Investigators should closely monitor both FVIII activity and ALT levels (eg, weekly to every 2 weeks for the first month) in order to determine if any detrimental effects on the efficacy or safety of BMN 270 have occurred. If co-medications are required during the course of the study, where possible, please check the National Center for Biotechnology Information LiverTox website for potential hepatotoxicity issues prior to prescribing ([NCBI, 2020](#)).

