9.7.3 Secondary Efficacy Variables

9.7.3.1 Factor VIII Replacement Therapy/Bleeding Episodes

Secondary efficacy variables include:

- Change in the annualized utilization (IU/kg/year) and infusion (number/year) rates of exogenous FVIII replacement therapy during Week 5 to Week 52 post-BMN 270 infusion from the baseline number and utilization of exogenous FVIII replacement therapy, for subjects receiving FVIII prophylaxis during the 12 months prior to study entry, or change in administration of exogenous FVIII replacement therapy Week 27 to Week 52 post-BMN 270 infusion for subjects receiving prior emicizumab prophylaxis.
- Change in the annualized number of bleeding episodes requiring exogenous FVIII replacement treatment (annualized bleeding rate, ABR) during Week 5 to Week 52 post-BMN 270 infusion for subjects receiving prior FVIII prophylaxis, or Week 27 to Week 52 post-BMN 270 infusion for subjects receiving prior emicizumab prophylaxis, from the baseline ABR during the 12 months prior to study entry.

Subjects must have high quality documented historical data available concerning previous bleeding episodes and hemophilia treatment over the previous 12 months in order to be eligible to enroll in the study. During the study, subjects will be asked at each study visit to

report the use of factor replacement therapy and the number of bleeding episodes since the previous visit. This information will be captured on the subject's diary or other subject records.

Subjects are strongly encouraged to immediately consult Investigator for guidance regarding exogenous FVIII administration for suspected bleeds or bleeding episodes within the first 30 days post-BMN 270 infusion.

In subjects who experience recurrent bleeding episodes, the Investigator and Medical Monitor will discuss whether to resume prior FVIII prophylaxis or use of emicizumab.

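### Section 9.3.3 lets the investigator or sponsor withdraw already-dosed subjects from the study for protocol breaches, which stops no study drug and gives up scheduled follow-up

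*Protocol*

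**What the plan says.** Section 9.3.3 (same wording on this point in the original protocol and Amendment 1) gives a non-exhaustive list of reasons for which the investigator or sponsor may withdraw a subject from the study. Two are "Subject requires medication or medical procedure prohibited by the protocol" and "Subject does not adhere to study requirements specified in the protocol". Neither mentions dosing status.

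The next bullet does. It allows withdrawal for erroneous enrolment or failed entry criteria only before dosing, and adds that "subjects who do not meet entry criteria but who erroneously receive BMN 270 should remain in the study for safety monitoring".

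A more general sentence in the same section reads: "A subject's participation in the study may be discontinued at any time at the discretion of BioMarin or of the Investigator". After such a discontinuation, the termination-visit tests are to be done when possible, and "every effort will be made to gather follow-up safety data if possible".

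Section 9.4.8 defines the first reason: "The following medications are prohibited starting 30 days before Screening and through the end of the study". The Amendment 1 list is any investigational therapy, fitusiran, concizumab and efavirenz. Section 9.3.5 plans 260 weeks of follow-up after infusion, and long-term safety is an objective in Section 8.

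**The concern.** In a trial with repeated dosing, withdrawal for a prohibited medicine or for non-adherence at least ends exposure to the study drug. Here exposure is complete on Day 1, and Section 9.2 describes the product as probably given only once. For a dosed subject, all that ends is scheduled observation.

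The triggers could be related to outcome. A subject whose expression is failing might seek another investigational product or one of the named hemophilia agents. Non-adherence is undefined and could include alcohol use, which Section 9.7.8.3 lists among possible causes of ALT elevation; Section 7.3 reports that early ALT elevation in 270-301 was associated with lower FVIII activity.

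Two things are at stake. One is the Week 49-52 value, which must be imputed if follow-up ends earlier. The other is the long-term safety record: Section 9.3.3.1 makes a cancer at any time after infusion a trigger for urgent DMC review, which depends on subjects still being seen. A statistical analysis plan cannot recover observations that the protocol allowed to stop.

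**Working it through.** **Passages side by side**

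| Dosed subject who... | What the protocol provides |
|---|---|
| was ineligible and dosed in error | should remain for safety monitoring (9.3.3) |
| is a treatment failure | may move to Q12W and End of Year visits in Years 2-5 (9.1) |
| needs a prohibited medicine or procedure | may be withdrawn from the study (9.3.3) |
| does not adhere | may be withdrawn from the study (9.3.3) |
| is discontinued at discretion | termination-visit tests and safety follow-up, both when possible (9.3.3) |

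All five have had the same exposure, but the protocol explicitly provides for continued follow-up only in the first two rows.

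**What happens to the primary endpoint.** The mITT population is all dosed subjects who were AAV5 antibody negative at Screening (Amendment 1 synopsis), so a withdrawn antibody-negative subject stays in. Under Section 14.2 of the original protocol, a missing Week 49-52 value takes the median of the subject's last 4-week window with a valid observation. The Amendment 1 text of that section is not in the supplied document.

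Let v be the carried-forward value and w the value that would have been seen. With 16 subjects, one withdrawal shifts the mean by (v − w)/16. The documents give neither v nor w, so I use the protocol's own reporting thresholds as assumed values:

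- v = 15, w = 5 IU/dL: (15 − 5)/16 = 0.625 IU/dL.
- v = 40, w = 5 IU/dL: (40 − 5)/16 = 2.19 IU/dL. This subject is also wrongly counted at or above 15, 25, 30 and 40 IU/dL, moving each proportion by 1/16 = 6.25 percentage points.

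The sign is not fixed. Section 7.3.1 describes a peak during months 6-12 and then a decline. A value carried forward from near the peak can overstate the result; one from before the peak can understate it.

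**What happens where withdrawn subjects drop out.** Section 14.2 also plans an observed-case sensitivity analysis. The stated power is checked first, with n = 16, effect size 0.8, 1-sided alpha 0.025 and a one-sample t-test:

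Power = 1 − F(t(0.975; n−1); n−1, 0.8√n), where F is the noncentral t distribution function. At n = 16 the noncentrality is 0.8 × 4 = 3.2 and power is 84.8%, which reproduces the stated 85%.

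If losses are unrelated to response, power is 82.1% with 15 subjects, 79.0% with 14, 75.4% with 13 and 71.4% with 12. The protocol gives no dropout rate, so one to four losses is an assumption.

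As an extreme bound, suppose the losses are exactly the lowest responders of 16 (normal data, 200,000 simulated trials):

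| Lowest responders removed | Mean standardised change (true 0.80) | 1-sided rejection rate if true change is 0 |
|---|---|---|
| 0 | 0.80 | 2.5% |
| 1 | 0.92 | 8.1% |
| 2 | 1.02 | 16.8% |
| 3 | 1.11 | 28.2% |

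This bounds the observed-case analysis, and later-year summaries of those still followed. It does not describe the primary analysis, where the subject is carried forward.

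**The case against.** A reader might infer that the plan removes poor responders. The documents do not support that. The bullets are permissive and poor response is not among them. Section 9.1 provides for treatment failures to continue with Q12W and End of Year visits. Section 9.7.3.1 has the investigator and Medical Monitor discuss "whether to resume prior FVIII prophylaxis or use of emicizumab", and Section 9.4.8.1 always allows FVIII for an acute bleed. A subject with failing expression therefore has options within the study that are not on the prohibited list. When a prohibited medicine is taken, Section 9.4.8 itself asks only that the sponsor be told.

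A reader might also infer that withdrawn subjects leave the primary analysis, so that the 8.1% above is its error rate. They do not leave it: ITT and mITT are defined by having been dosed. The carry-forward rule is a separate matter, and observed-case and MMRM sensitivity analyses are already planned.

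Nor does the rule in Section 9.3.4, "Subjects who withdraw from the study after receiving BMN 270 will not be replaced", add to the safety concern. Replacing a subject would not restore the lost subject's follow-up.

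Follow-up after withdrawal is not nil. In the original protocol, the termination visit (Section 12.8) covers FVIII activity, liver tests, inhibitors and patient-reported outcomes, and Section 10.7 asks for later deaths and SAEs thought related, and for cancers that come to the investigator's attention.

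All of this stands, and it narrows the point. It leaves the wording gap: dosed subjects may be withdrawn for two reasons that serve no treatment purpose, and afterwards follow-up is one visit and best effort instead of a schedule.

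**Conclusion.** The point holds as a design weakness that should be corrected; it is not a fatal flaw. Section 9.3.3 allows avoidable loss of follow-up in dosed subjects and is inconsistent with its own rule for subjects dosed in error. The missing data could be related to outcome, but the documents do not show that they would be.

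The number affected is unknown. Per withdrawn subject, the primary mean moves by (v − w)/16, which is 0.6 to 2.2 IU/dL under the assumed values and could go either way. Observed-case power falls from 84.8% to 82.1% with the first random loss. The selective-loss figures are a worst case for the observed-case analysis only. For safety, the loss is whatever remained of that subject's 260 weeks of scheduled visits.

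The imputation rule, termination visit and post-study reporting are taken from the original protocol and assumed unchanged, because those Amendment 1 sections are not in the supplied text.

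**What to change.** Revise Section 9.3.3 in three places:

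- Limit investigator- or sponsor-initiated withdrawal for a prohibited medicine or procedure, or for non-adherence, to subjects who have not received BMN 270.
- Bring the discretion sentence and the open-ended lead-in to the list into line. Editing the two bullets alone would leave the same power in place.
- State that a dosed subject remains in follow-up for FVIII activity, bleeding, hemophilia therapy use and safety, at least on the existing Q12W and End of Year schedule after Week 52, unless he withdraws consent or data permission or is lost to follow-up. Record prohibited medicine use as a deviation.

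This changes no rule on which medicines a subject may receive; it governs only whether he continues to be observed. It adds no visits beyond those planned. The cost is a few sentences in one section, plus a decision on how values obtained after a prohibited medicine are handled in the analysis. It will not secure data from a subject who stops attending, but it removes the protocol's own reason for ending his follow-up.
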